1. BACKGROUND AND RATIONALE

Glaucoma is a leading cause of irreversible blindness. The disease is characterized by elevated intraocular pressure (IOP), cupping of the optic disc, or a diminished visual field. Large prospective studies have shown that the risk for glaucomatous progression is significantly reduced when IOP is lowered and that each 1mmHg reduction in IOP is associated with an approximate 10% decrease in the risk for progression

It is firmly entrenched in the traditional treatment paradigm to start with pharmacotherapy. However, pharmacotherapy is not benign and has been well documented to have a number of significant challenges. Once medications have failed, the conventional next step is to perform a trabeculectomy operation which is a intraocular penetrating operation.

The iStent is a FDA and HSA approved micro-bypass stent device that is implanted with an ab interno approach (inserted from inside the eye rather than from outside the eye) that bypasses the trabecular meshwork (filtration membrane of the aqueous fluid exit pathway) and reroutes aqueous from the anterior chamber directly into canal of Schlemm and out of the eye without disrupting the conjunctival and scleral eye surface.

It works well in open angle glaucoma, where the drainage angle is open and has been shown to reduce the eye pressure and number of medications required at 2 years post operation. This device has not been used in angle closure glaucoma because of the lack of space when the drainage angle is narrow. However, if this device is combined with lens extraction or cataract surgery, then the drainage angle is widened and the device can be safely implanted.

Cataract surgery or phacoemulsification lens extraction is known to reduce the eye pressure in certain cases, but not all cases. It is more effective in IOP lowering in angle closure cases. It is not standard care to perform phacoemulsification lens extraction in angle closure glaucoma. The standard of care is usually a combined operation of phacoemulsification with trabeculectomy or trabeculectomy alone. Trabeculectomy, however, has a significant complication rate that includes infection, bleeding, bleb failure, bleb infections, hypotony and suprachoroidal haemorrhages.

The purpose of this study was to compare the IOP-lowering efficacy and safety of phacoemulsification alone and phacoemulsification and micro-bypass stent implantation in eyes with primary angle closure and primary angle closure glaucoma.

1.1. General Introduction

The iStent is a FDA and HSA approved micro-bypass stent device that lowers the IOP. It needs to be combined with phacoemulsification lens extraction in angle closure glaucoma in order to create enough space for the iStent to be safely inserted. Both phacoemulsification and phacoemulsification with iStent are likely to reduce the IOP, but we hypothesis that the combined group will perform better, leading to better IOP control using less medications at 1 year.

1.2. Rationale and justification for the Study

The iStent has never been studied in primary angle closure or primary angle closure glaucoma. In Singapore or Chinese populations, primary angle closure and primary angle closure glaucoma is much more common than in the African and Caucasian populations. All iStent studies have been in patients with open angles, which is more common in the West. We have therefore selected this population for our study, which is more relevant in the Singapore context.

It is becoming more popular to remove the lens with phacoemulsification in angle closure glaucoma as a form of treatment to reduce IOP. It works by increasing the amount of space in the angle and the ultrasound component may also have an effect in increasing outflow. Interestingly, some patients also have an increase in IOP after surgery and some patients have no change in IOP after surgery.

The iStent is a FDA and HSA approved micro-bypass stent device that bypasses the trabecular meshwork (filtration membrane of the aqueous fluid exit pathway) and reroutes aqueous from the anterior chamber directly into canal of Schlemm and out of the eye. It lowers the IOP by increasing the outflow of fluid from the eye from the micro-bypass. In angle closure, the lens has to be removed to create enough space for the iStent to be inserted.

We therefore plan to compare the effects of phacoemulsification alone, to phacoemulsification with iStent implantation in patients with angle closure and angle closure glaucoma.

If the IOP can be better controlled with the phaco + iStent, then it can reduce the need for IOP lowering medications, and reduce the need for further invasive glaucoma surgery such as trabeculectomy, that have higher risks of adverse events.

We will perform a randomised controlled study, blinded to the patient and the IOP checking staff. Our hypothesis is that the phaco-iStent combined group will have a lower mean IOP at 1 year compared to the phacoemulsification alone group and that more patients will have an IOP of <21mmHg at 1 year in the combined phaco-iStent group, and the phaco-iStent group will require less medications at 1 year.

a. Rationale for the Study Purpose

Phacoemulsification alone reduces the IOP in the first year, but tends to return to baseline after 1-2 years. A meta-analysis comparing phacoemulsification with phacoemulsification with iStent found it to be in favour to the phacoemulsification with iStent group (SMD=-0.46). There have been 4 randomised controlled trials comparing phacoemulsification with phacoemulsification + iStent in primary open angle glaucoma and 6 studies evaluating phacoemulsification + iStent again in open angle glaucoma. The four randomised controlled trials showed the phaco+iStent group to have a greater IOP reduction. (17% vs 9%, 27% vs 16%, 10% vs 8%, 8% vs 5%)

There have been no studies evaluating phacoemulsification + iStent in primary angle closure

or primary angle closure glaucoma.

This study will be the first randomised controlled trial in primary angle closure or primary angle closure glaucoma. This will also be the first iStent trial in Singapore on Singaporeans.

This is important because primary angle closure is much more common in the Singaporean Chinese population and the most common cause of irreversible bilateral blindness in the Asia. Phacoemulsification has become a more common procedure to help manage this condition although trabeculectomy or combined phacotrabeculectomy is still the gold standard surgery. Phacoemulsification with iStent may be a suitable operation for this condition that can avoid the higher risks of the trabeculectomy and yet have a better IOP control than phacoemulsification alone.

b. Rationale for Doses Selected

Phacoemulsification with 1 iStent will be used because in the open angle studies, it had a improved IOP control compared to phacoemulsification alone. 2 iStents or 3 iStents can be inserted and have been reported to have good response, but with very limited data to show any added benefit given the additional cost.

c. Rationale for Study Population

The patients will be selected from the clinic patient population. Primary angle closure and primary angle closure glaucoma have been chosen because the disease is more relevant and common in the Singaporean context compared to the western countries. Also this disease has not been studied using the iStent.

d. Rationale for Study Design

Randomised controlled trial with blinding to the patient and the IOP measurer and reader with adequate sample size to compare both groups is the best way to answer our research question.

2. HYPOTHESIS AND OBJECTIVES

2.1. Hypothesis

Phacoemulsification with micro-bypass stent has a better IOP lowering effect compared to phacoemulsification alone in primary angle closure and primary angle closure glaucoma at 1 year after surgery.

2.2. Primary Objectives

To assess the efficacy of the iStent trabecular micro-bypass stent (Glaukos Corporation, Laguna Hills, CA) in combination with cataract surgery in subjects with primary angle closure and mild to moderate primary angle closure glaucoma

2.3. Potential Risks and benefits:

a. End Points – Efficacy

The primary outcome is: unmedicated IOP \leq 21mmHg at 1 year and mean IOP at 1 year.

A secondary outcome measure is medication reduction at 1 year post operation

b. End Points - Safety

Safety measures include best corrected visual acuity, slit lamp observations, complications and adverse events

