5. STUDY DESIGN

Single centre, randomised prospective trial, the patient and the IOP checking staff will be blinded. Randomised by random envelope shuffle technique.

1:1 ratio allocation

2 arms: phacoemulsification alone and phacoemulsification and iStent.

16 patients in each arm, 32 patients in total.

The post-operative management is the same for both arms

After operation the patient will be followed up at day 1, week 1, week 2, months 1, 3, 6 and 12.

At each visit the patient will have the following tests: Tonometry (IOP check) - Not to be taken by the operating surgeon, to be taken by 2 people, one IOP checker and one reader.

The target IOP is 18mmHg for patients with PAC or mild PACG. If the IOP rises above 18mmHg in 2 consecutive visits then the original glaucoma medication(s) will be reinstated or as per the clinicians discretion.

IOP at 12 months will be the primary outcome measure. The target pressure will be based on the Asia Pacific Glaucoma Guidelines. For PAC with high IOP and PAS and early PACG, the target will be $>/=20\%$ from base line or 18mmHg whichever is lower. b. The Asia Pacific Glaucoma Guidelines classifies “PAC with High IOP and PAS” to be “glaucoma with moderate 5-year risk for visual loss” and to treat the IOP with a target of $>/=20\%$ or 18mmHg whichever is lower.

The target IOP is 18mmHg for patients with PAC or mild PACG. If the IOP rises above 18mmHg in 2 consecutive visits then the original glaucoma medication(s) will be reinstated or as per the clinicians discretion.

The patient will be masked to the treatment arm given, but the investigators will not be masked.

The procedure will be performed by 2 surgeons: [name] and [name], the follow up visits and monitoring of pressure will be done by the investigation team.

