11. SAMPLE SIZE AND STATISTICAL METHODS

11.1. Determination of Sample Size

Details on sample size calculation and the means by which data will be analysed and interpreted.

In particular, specify all of the following:

- Null Hypothesis
Phacoemulsification with micro-bypass stent has no difference in effect on IOP compared to phacoemulsification alone in primary angle closure and primary angle closure glaucoma at 1 year after surgery.
- Alternate hypothesis
Phacoemulsification with micro-bypass stent has a better IOP lowering effect compared to phacoemulsification alone in primary angle closure and primary angle closure glaucoma at 1 year after surgery.
- Type I error rate = 0.05
- Type II error rate = 0.2

Sample Size Calculation:

Based on published data of phaco and phaco iStent RCT in open angle glaucoma:

Mean IOP for control at 1 year (phaco only group) – 19.2mmHg +/- 3.1

Mean IOP for combined group at 1 year (phaco+istent group) – 16.6mmHg +/-3.5

Alpha = 0.05

Power = 0.80

SD: 2.4

Difference: 2.6

Sample size = 14 in each arm

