11.2. Statistical and Analytical Plans

a. General Considerations

Independent t- tests will be used to compare both groups at 12 months post operation

“Success” will be defined as IOP unmedicated IOP</=21mmHg at 1 year and unmedicated IOP reduction of >/=20% at 1 year, with no additional anti-glaucomatous medications at 1 year. The rational for 20% reduction is based on published RCT trials that use 20% as a standard reduction expected from this device. The same reduction percentage is used for comparison to other published data.

Chi-square test will be used to compare success versus failure in both groups.

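### Section 2.3 lists two primary outcomes with no success rule, and the only responder test stated, in 11.2, uses a different definition from the binary outcome listed there.

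*Protocol*

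**What the plan says.** Section 2.3 a (End Points - Efficacy) introduces the primary outcome in the singular and then gives two: the proportion with unmedicated IOP at or below "21mmHg at 1 year and mean IOP at 1 year". It gives no rule for combining them.

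Section 5 (Study Design) says "IOP at 12 months will be the primary outcome measure" and mentions no responder outcome in that sentence. Section 6 also frames the comparison as IOP at one year.

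Section 11.1 has a single null hypothesis, "Phacoemulsification with micro-bypass stent has no difference in effect on IOP compared to phacoemulsification alone", and a single "Type I error rate = 0.05". Its sample size uses a difference of 2.6 mmHg, SD 2.4 and power 0.80, and gives 14 per arm. Sections 3.1 and 5 plan 16 per arm.

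Section 11.2 states two tests. Independent t-"tests will be used to compare both groups at 12 months post operation"; the variable is not named, but the natural reading is IOP. The second is on success: "Chi-square test will be used to compare success versus failure in both groups". Success there needs unmedicated IOP at or below 21 mmHg and also "unmedicated IOP reduction of >/=20% at 1 year, with no additional anti-glaucomatous medications at 1 year".

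Two other provisions bear on the point. Patients enter on at least one hypotensive medication (3.3). After surgery, "If the IOP rises above 18mmHg in 2 consecutive visits then the original glaucoma medication(s) will be reinstated", or the clinician may decide otherwise (section 5).

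**The concern.** The protocol contradicts itself in two places. The first is the number of primary outcomes: two in 2.3, apparently one in sections 5 and 11.1. The second is the responder outcome: 2.3 lists one definition as primary and 11.2 tests another.

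This is not detail that can be left to an analysis plan, because an analysis plan cannot carry out both versions. As written, the trial could be called positive on mean IOP, on the 2.3 responder rate or on the 11.2 success rate, and a reader could not tell which of these was fixed in advance. The stated alpha and power would describe only one of them.

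**Working it through.** **1. The plan's own figure.** Inputs from 11.1: difference 2.6, SD 2.4, alpha 0.05, power 0.80.

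n per arm = 2 × (z₁₋α/₂ + z₁₋β)² × (SD/difference)²

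- Two-sided: 2 × (1.960 + 0.842)² × (2.4/2.6)² = 13.4, rounded up to 14. This matches the protocol.
- One-sided: 2 × (1.645 + 0.842)² × (2.4/2.6)² = 10.5, rounded up to 11. This does not match.

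The 14 is therefore a two-sided calculation on the mean alone. At the planned 16 per arm the two-sided t-test has power 0.84.

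**2. How the two responder definitions differ.** A 20% reduction requires a final IOP of at most 0.8 × baseline. This equals 21 when baseline = 21/0.8 = 26.25 mmHg. Below that baseline the 11.2 rule is the stricter one by value. Entry requires IOP above 21 mmHg (3.3), so such baselines are admitted. For example, take a baseline of 24 and an unmedicated IOP of 20 at 1 year with no drops. Under 2.3 this is a responder. Under 11.2 the reduction is 4/24 = 16.7%, so it is a failure.

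Reinstatement may narrow the gap. If every patient above 18 mmHg were back on drops and counted as a failure, the rules would differ by value only below 18/0.8 = 22.5 mmHg.

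**3. Both must succeed.** Assumptions, because the protocol gives no responder rates: normal IOP, means 19.2 and 16.6 taken as off-drops values, SD 2.4 in both arms, one common baseline, 16 per arm, no reinstatement. The response probability is Φ((limit − mean)/2.4).

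- Limit of 21: Φ(0.75) = 0.77 against Φ(1.83) = 0.97.
- 20% rule at baseline 22, limit 17.6: Φ(−0.67) = 0.25 against Φ(0.42) = 0.66.

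Joint power of the t-test and chi-square on the same patients, 200,000 simulated trials per setting:

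| Responder rule | Uncorrected chi-square | Continuity-corrected |
|---|---|---|
| IOP at or below 21 | 0.33 | 0.09 |
| 20% rule, baseline 22 | 0.65 | 0.51 |
| 20% rule, baseline 24 | 0.62 | 0.43 |
| 20% rule, baseline 26 | 0.38 | 0.13 |

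**4. Either suffices.** Both arms were given the same mean (16.6, 17.9 or 19.2) and the same SD (2.4, 3.1, 3.3 or 3.5), with the four limits above and each test at 0.05. The chance of at least one false positive was about 5-9% uncorrected and 5-6% corrected. Two independent tests would give 1 − 0.95² = 9.75%.

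**5. What reinstated drops would do to the mean.** The protocol gives no size for this effect, so reductions of 10, 20 and 30% are assumptions. They are applied to patients above 18 mmHg at 12 months, as a proxy for the section 5 rule, with SD 2.4.

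| Share reinstated | t-test power (10 / 20 / 30%) | Joint power, limit of 21, uncorrected |
|---|---|---|
| Half | 0.79 / 0.56 / 0.27 | 0.43 / 0.28 / 0.09 |
| All | 0.80 / 0.37 / 0.05 | 0.60 / 0.24 / 0.03 |

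**The case against.** The strongest reply is that the protocol is in substance written for one outcome. The hypothesis in 2.1, section 6 and the sample size in 11.1 all concern the IOP effect at 1 year, and any rule for combining outcomes may sit in an analysis plan that is not shown. Part of this stands. It makes mean IOP the natural choice of primary, and it limits the claim to what the protocol states: a test of the 2.3 responder outcome may exist elsewhere. It does not remove the contradiction, because 2.3 still lists two outcomes and 11.2 still defines success differently.

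Three further objections also stand in part.

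- The word joining the two outcomes in 2.3 could be taken to mean that both must succeed. It reads as a list, and nothing in the protocol makes it a decision rule. The joint-power figures show what one reading would cost; they do not describe a stated plan.
- Section 5 says IOP, not mean IOP, so by itself it is not decisive that the responder outcome was meant to be dropped.
- In practice the two responder definitions can classify patients alike: always by value at baselines of 26.25 mmHg or more, and possibly at lower ones once reinstated patients count as failures.

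**Conclusion.** The point holds as a contradiction within the protocol. Two outcomes are listed as primary without a success rule, one alpha and one sample size serve only the mean, and no test is stated in this protocol for the binary outcome as 2.3 defines it. That conclusion rests on the text alone.

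The size of the consequence depends on assumptions. At SD 2.4 with off-drops IOP and no reinstatement, requiring both outcomes would lower power from 0.84 to between 0.33 and 0.65 with an uncorrected chi-square. Allowing either would raise type I error modestly, to at most about 9%, and hardly at all with continuity correction.

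Two stronger readings should not be drawn.

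- A reader might repeat the calculation with the quoted SDs of 3.1 and 3.5 and report joint power of 0.22 to 0.39. Much of that loss comes from a separate matter, the SD of 2.4 used in 11.1: at those SDs the t-test alone has only 0.58.
- A reader might suppose that ignoring reinstatement gives the worst case. It does not if the mean includes medicated values: joint power for the limit of 21 can then be below 0.33, as the last table shows.

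The matter should be corrected, but it does not invalidate the design, since the sample size points clearly to the mean.

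**What to change.** In 2.3, name mean IOP at 12 months as the single primary outcome, since this is what the sample size was computed for. State the sidedness, which no section gives at present; two-sided reproduces the stated 14 per arm. State whether the mean is on or off medication. Make the responder proportion secondary, with one identical definition in 2.3 and 11.2 that says what unmedicated and additional mean and from which baseline the 20% is counted. Align the rationale in 1.2, which uses a limit below 21 and does not mention medication.

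If two primaries are kept, state either that both must succeed or how alpha is split, and restate the power for that rule.

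Cost: with a single primary, the sample size calculation and alpha need no change, but this is more than an edit of wording. The only explicitly unmedicated outcome loses primary status. If the mean includes values on reinstated medication, the expected difference and its power will be lower than stated, by an amount that depends on the effect of the drops. If the 19.2 and 16.6 mmHg in 11.1 already include medicated values, the loss shown above is overstated.

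### The 80% power in section 11.1 is derived for mean IOP only and does not hold for the other listed primary outcome, unmedicated IOP at or below 21 mmHg

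*Protocol*

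**What the plan says.** Section 2.3 a lists two outcomes under the primary heading: unmedicated IOP at or below "21mmHg at 1 year and mean IOP at 1 year". Section 1.2 also carries a responder hypothesis, that more patients in the combined arm will be below 21 mmHg at 1 year. Section 5, by contrast, states that "IOP at 12 months will be the primary outcome measure".

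Section 11.1 gives "Type I error rate = 0.05" and "Type II error rate = 0.2". It quotes published open-angle data ("Mean IOP for control at 1 year (phaco only group) – 19.2mmHg +/- 3.1", and 16.6 mmHg with SD 3.5 for the combined group), then uses a difference of 2.6 and an SD of 2.4 to reach "Sample size = 14 in each arm". Sections 3.1 and 5 plan 16 per arm. No responder rate and no responder power appears anywhere.

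Section 1.2 d describes a randomised trial "with adequate sample size to compare both groups is the best way to answer our research question". Section 11.2 defines success as unmedicated IOP at or below 21 mmHg plus an unmedicated reduction of at least 20% with no additional medication, and says "Chi-square test will be used to compare success versus failure in both groups".

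**The concern.** The sample size rests on one of the two listed primary outcomes, while the type II error is given once, without limiting it to that outcome. Cutting a continuous measurement at a threshold usually loses power, and 16 per arm is small for comparing two proportions.

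A reader who sees a trial described as adequately sized, with a type II error of 0.2, may take a non-significant responder comparison as evidence that the stent adds nothing. Sections 1.2 and 1.2 a present this as the first study of the device in angle closure, so such a misreading could carry weight. If both primary outcomes must succeed, which the protocol does not settle, the power of the whole trial cannot exceed the power of the responder comparison.

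**Working it through.** **Inputs**, all from section 11.1 unless noted: control 19.2 mmHg (SD 3.1); combined 16.6 mmHg (SD 3.5); SD used 2.4; difference 2.6; alpha 0.05; power 0.80; 16 per arm (sections 3.1 and 5). Sidedness is not stated. Two-sided testing reproduces the plan's figure and one-sided does not (it gives 11).

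**Step 1. The plan's own figure.** n per arm = 2 × [(1.960 + 0.842) × 2.4 / 2.6]² = 13.4, rounded up to 14. This reproduces. At 16 per arm the power for the mean, with SD 2.4, is 86.5% (normal) or 84.2% (t).

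**Step 2. Responder rates from the same values.** Assume IOP is normal and treat the quoted means as unmedicated. Then P(IOP ≤ 21) = Φ((21 − mean)/SD).
- Control: Φ(1.8/3.1) = 71.9%. Combined: Φ(4.4/3.5) = 89.6%.
- With SD 2.4 in both arms: Φ(1.8/2.4) = 77.3% and Φ(4.4/2.4) = 96.7%.

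**Step 3. Power at 16 per arm for the 21 mmHg cut.** Normal approximation with the arm SDs: mean rate 0.8075; null SE = √(2 × 0.8075 × 0.1925/16) = 0.139; alternative SE = 0.136; power = Φ((0.176 − 1.96 × 0.139)/0.136) = 23.8%. Exact enumeration of all pairs of binomial counts gives 24.9% (first row of the table).

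**Step 4. A lower effective cut.** Two parts of the protocol could lower it.
- Section 5 reinstates medication, or leaves it to the clinician, when IOP exceeds 18 mmHg at two consecutive visits. A re-medicated eye has no unmedicated IOP at 1 year, so 18 serves as an illustrative bound.
- Section 11.2 also requires a 20% reduction. With an assumed fixed baseline of 22 mmHg the cut is 0.8 × 22 = 17.6. With 28 mmHg it is 22.4, so 21 governs and the first row applies. The documents give no baseline mean.

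Exact power at 16 per arm, two-sided 0.05:

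| Cut (mmHg), SD | Control | Combined | Chi-square, uncorrected | Continuity-corrected | Fisher |
|---|---|---|---|---|---|
| 21, SDs 3.1/3.5 | 71.9% | 89.6% | 24.9% | 9.6% | 13.1% |
| 21, pooled SD 3.31 | 70.7% | 90.8% | 31.3% | 13.0% | 17.5% |
| 21, SD 2.4 | 77.3% | 96.7% | 34.2% | 9.4% | 18.3% |
| 18, SDs 3.1/3.5 | 34.9% | 65.5% | 42.2% | 28.1% | 28.1% |
| 18, SD 2.4 | 30.9% | 72.0% | 67.4% | 52.5% | 52.5% |
| 17.6, SDs 3.1/3.5 | 30.3% | 61.2% | 43.3% | 28.8% | 28.8% |
| 17.6, SD 2.4 | 25.2% | 66.2% | 67.1% | 52.0% | 52.0% |

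Pooled SD = √((3.1² + 3.5²)/2) = 3.31.

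**Step 5. Scale.** From a 72% control rate, even a 100% rate in the combined arm gives only about 70% power (uncorrected chi-square). At 71.9% v 89.6%, 80% power would need about 78 per arm. One-sided testing at 0.05 raises power for the 21 mmHg cut to 35–49%, still short.

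**Step 6. Precision.** SE of the risk difference at the planning rates = √(0.719 × 0.281/16 + 0.896 × 0.104/16) = 0.136, so the 95% interval is about ±1.96 × 0.136 = ±27 points around an 18-point difference.

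**The case against.** **The protocol never claims 80% power for the responder outcome.** The type II error in section 11.1 sits beside hypotheses about the effect on IOP, section 2.1 has the same hypothesis, and section 5 names IOP at 12 months as the primary outcome measure. The remark about adequate size in section 1.2 d is general. This stands: the document makes no explicit false claim about responder power, and its sample-size arithmetic is not wrong. It does not remove the point, because section 2.3 a still lists the responder outcome as primary and nothing limits the power statement to the mean.

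**A reader might infer that responder power simply is 25%, so a real benefit would be missed three times in four.** The documents do not support that as a fixed property. They give no responder rates and do not say that the published means are unmedicated, and the rule in section 5 may move the effective cut well below 21 mmHg. The 25% is the lowest of the uncorrected chi-square results. The SD matters too: for the section 11.2 success rule at an assumed baseline of 22 mmHg, power is 43% with SDs 3.1/3.5 and 67% with SD 2.4.

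**The test belongs to another endpoint.** Section 11.2 attaches the chi-square test to composite success, not to the 21 mmHg outcome alone. This also stands. The first three rows of the table therefore assume that the same test is applied to the section 2.3 a outcome, and the no-additional-medication part of success cannot be modelled from the documents.

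**Conclusion.** The point holds as a mismatch between the listed primary outcomes and the power statement. The 80% is a property of the mean IOP comparison only. For the responder outcome at 16 per arm, two-sided uncorrected chi-square power is about 25% with SDs 3.1/3.5 and 34% with SD 2.4 at the 21 mmHg cut, and roughly 25–67% once a lower effective cut is allowed. Continuity-corrected and Fisher tests give less in every case. In type II error terms this is about 0.33 to 0.75 against the stated 0.2, and no scenario examined reaches the stated level.

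These figures assume normal IOP, open-angle means that carry over and count as unmedicated, complete data in 16 per arm, and, for the lower cuts, an illustrative 18 mmHg bound or an assumed baseline. The conclusion that the responder outcome is not powered is firmer than any single figure.

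**What to change.** - In section 11.1, state that the 80% power applies to mean IOP only, on the SD of 2.4 used there. (That SD is below both quoted arm SDs, which is a separate question.) Add that the responder outcome is not powered at 16 per arm, and give the range of about 25–67% with its assumptions rather than a single design value.
- Reconcile sections 2.3 a, 5 and 11.2 on which IOP outcome is primary, how the responder outcome is defined, and how an eye back on medication counts. One option is mean IOP as the sole primary outcome with the responder outcome as supportive.
- Report the responder result as a risk difference with a 95% interval (about ±27 points at the planning rates), and state that a non-significant result does not show absence of effect.
- Do not enrol more patients on this account. Do not choose the uncorrected chi-square test merely because it has more power: its exact size at 16 per arm is about 5.8% when both rates are 0.72. The version of the test can be left to the analysis plan.

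The cost is wording only, with no new patients, visits or data. The downside is a less favourable stated power.

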3. STUDY POPULATION

3.1. List the number of subjects to be enrolled.

All patients will be recruited from the ophthalmology and visual science department of Khoo Teck Puat Hospital. There will be no restriction on race. Children will be excluded from this study as the surgeons have limited experience operating on children.

The project aims to recruit 32 patients, 16 in each arm of the randomisation, of phacoemulsification alone and phacoemulsification and iStent Implant.

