3.3. Inclusion Criteria

Provide informed consent

Previous diagnosis of PAC or PACG

IOP above 21mmHg at 3 separate visits

On 1 or more hypotensive medications

Pre-operative VA of no better than 6/12

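### Secondary medication outcome: section 2.3 names a reduction, sections 1.1 and 1.2 a number at 1 year, and adjusting for the pre-operative number would make the two give one answer (minor)

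*Protocol*

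**What the plan says.** - Section 2.3 a, the only list of efficacy end points: "A secondary outcome measure is medication reduction at 1 year post operation". It does not say whether this means a change in count, a percentage or a proportion of patients.
- Section 1.1 expects the combined procedure to do better, "leading to better IOP control using less medications at 1 year". Section 1.2 adds that "the phaco-iStent group will require less medications at 1 year". Both read as a comparison of the number in use at 1 year.
- Section 3.3 admits patients "On 1 or more hypotensive medications", so the starting number can vary.
- Section 5 says that if pressure stays above the target at two consecutive visits, "the original glaucoma medication(s) will be reinstated or as per the clinicians discretion". This ties the 1-year number to the starting number.
- Section 3.1: "The project aims to recruit 32 patients, 16 in each arm of the randomisation".
- Section 11.2, under general considerations: "Independent t- tests will be used to compare both groups at 12 months post operation". No variable is attached to the test and no covariate is mentioned. The hypotheses and sample size in section 11.1 concern IOP only.

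**The concern.** A reduction is the starting number minus the number at 1 year. The hypothesis in the introduction concerns the number at 1 year alone. If the full starting regimen comes back or nothing does, the two variables carry the starting number in opposite directions. An arm that happens to start on more drops has more to lose, so it looks better on reduction. It also has more to be put back on, so it looks worse on the 1-year number. An unadjusted t-test removes this from neither.

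Less need for medication is one of the benefits that section 1.2 puts forward for the stent. With 16 per arm, whether that benefit reaches significance could depend on which variable is tabulated. If the choice were made after seeing the data, the false-positive rate would exceed 5%.

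**Working it through.** **The plan's own figure.** Section 11.1 gives 14 per arm for a difference of 2.6 and an SD of 2.4 mmHg. It reproduces: 2 × (1.960 + 0.842)² × (2.4/2.6)² = 15.70 × 0.852 = 13.4, rounded up to 14. It concerns IOP. The protocol gives no mean, SD, effect or sample size for medications, so what follows rests on assumptions.

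**How the two estimates relate.** Let B be the pre-operative number, C the number at 12 months and R = B − C. Then

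(mean R, stent − mean R, control) = (mean C, control − mean C, stent) − (mean B, control − mean B, stent).

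The last bracket has expectation zero under randomisation, so both estimates target the same effect. In a single trial they differ by exactly the imbalance in B, whose SD is SD(B) × √(2/16) = 0.354 × SD(B):

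- B is 1–2, equally likely: SD(B) 0.50, imbalance SD 0.18 drops
- B is 1–3, equally likely: SD(B) 0.82, imbalance SD 0.29
- B is 1–4 with 40/30/20/10%: SD(B) 1.00, imbalance SD 0.35

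**A central restart rate (assumption).** The share above 18 mmHg, from the section 11.1 means and SDs and a normal distribution, is:

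- control: 1 − Φ((18 − 19.2)/3.1) = 65.1%
- stent: 1 − Φ((18 − 16.6)/3.5) = 34.5%

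This is one time point from open-angle data and only a stand-in for the two-visit rule in section 5. Squaring it (independent visits, an extreme case) gives about 42% v 12%. The true difference at the central rates is 1.5 × 0.306 = 0.46 drops (B 1–2) or 2.0 × 0.306 = 0.61 drops (B 1–3 and 1–4).

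**Simulation.** 40,000 trials of 16 v 16 per setting, two-sided 5% t-tests on C and on R. The table gives the share of trials in which exactly one of the two is significant, as the range over the three distributions of B.

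| Restart rate, control v stent | All or none | One drop at a time |
|---|---|---|
| 50% v 50% (no effect) | 5–7% | 7–9% |
| 50% v 40% | 7–9% | 11–16% |
| 65% v 50% | 10–12% | 15–23% |
| 65.1% v 34.5% | 18–23% | 25–39% |
| 42% v 12% | 23–28% | 29–47% |
| 90% v 20% | 2–7% | under 1% |

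With no effect, each test alone is at about 5%. Reporting whichever is significant gives about 8–9% under all-or-none return.

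**Adjusting for B.** Suppose C = a + τ·arm + β·B + e. Then B − C = −a − τ·arm + (1 − β)·B − e. The residuals are the same apart from sign, so the size of the effect, its standard error and its p-value are identical. The simulation confirmed this in every setting.

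Results at 65.1% v 34.5%, all or none:

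| B | SD of estimate: count / reduction / adjusted | Power: count / reduction / adjusted |
|---|---|---|
| 1–2 | 0.28 / 0.28 / 0.27 | 36 / 36 / 37% |
| 1–3 | 0.39 / 0.39 / 0.37 | 33 / 33 / 36% |
| 1–4 | 0.42 / 0.42 / 0.38 | 30 / 30 / 34% |

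Elsewhere, compared with the better of the two unadjusted tests, the gain ran from about −2 points (27.5% to 25.3%; 30% v 10%, all or none, B 1–2) to about +15 (51% to 66%; 65.1% v 34.5%, one at a time, B 1–4). With no effect the adjusted test rejected in 4.8–5.1% of trials.

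**The case against.** - **No contradiction.** Section 2.3 is the only list of end points and names one medication outcome. Sections 1.1 and 1.2 are introductory prose, and the formal hypothesis in section 2.1 does not mention medications. A larger reduction and fewer drops point the same way. This stands: a reader might infer two competing definitions, but the text shows only loose wording for one idea.
- **Detail for the SAP.** Count or change, and the choice of covariate, are often settled there. This stands in part. The protocol does, however, word the outcome in two ways and name an unadjusted method, and both are in the document at hand.
- **The t-test is not assigned to this outcome.** Correct. A reader might infer that an unadjusted t-test on medications is planned. Section 11.2 does not say so; it is only the sole test named for means.
- **Different significance is a weak measure of harm.** In the central setting each test has only 30–36% power, so results near 0.05 often split. Under all-or-none return the two were never both significant in opposite directions, and their estimates differed in sign in 3–7% of trials in the central setting. This stands, and keeps the point minor.
- **The common-slope model is not exact.** Under all-or-none return, the slope of C on B is 0.651 in one arm and 0.345 in the other. True, but with 1:1 randomisation the comparison kept its 5% error rate, and the equality of count and reduction does not depend on the slopes.

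**Conclusion.** This is a minor point on a secondary outcome. The two wordings agree in direction and in expected effect. In one trial of this size they can still give different p-values, because the starting number varies and no adjustment is named.

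It is tempting to attach a single frequency, such as one trial in five, to this trial. The documents do not support it. That figure needs a distribution of starting drops, a restart rate and a restart pattern, and the protocol gives none of these. What can be said is conditional:

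- all-or-none return: about 5–7% with no effect and about 10–28% with a moderate effect, with lower values when the effect is very small or very large
- one-by-one return: up to about 47%

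The case for change rests less on these shares than on the algebra. One covariate makes the choice between count and reduction irrelevant to the result, and usually adds a little precision.

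**What to change.** - Section 2.3: name one variable, the number of IOP-lowering medications in the study eye at 12 months. Use the same phrase in sections 1.1 and 1.2.
- Section 11.2: compare it between arms in a linear model with arm and the pre-operative number of medications. The result may be presented as a count or as a reduction, since the effect and p-value are the same.
- State that the pre-operative number is recorded. Section 3.3 requires at least one medication but does not say that the count is captured; any reduction outcome needs it anyway.

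The cost is a few lines of text and one degree of freedom (29 instead of 30 with 32 patients). No extra visit or measurement is needed, and the rule for restarting medication is not touched.
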